Age is a major factor that determines the prognosis of patients with untreated AML. The treatment of acute myeloid leukemia (AML) in older patients has not improved significantly in recent years when compared with the considerable progress that has been made in younger patients (1-3). AML occurring in patients ≥ 60 years of age continues to be associated with an extremely poor prognosis. Using a standard induction combination such as the "3+7" regimen (ara-C plus an anthracycline), the complete remission (CR) rate is 40% to 50%, the mortality 20% to 40%, and remission durations are usually transient and rarely last more than 12 months. The median time from treatment with the "3+7" regimen to death is 5 to 10 months and less than 10% of patients stay in remission at 3 years (4). Patients who are ≥ 70 years of age in particular tolerate 3+7 induction regimen very poorly with even worse results [20]. The reasons for this difference in outcome when compared to younger patients are multiple. Differences in the biology of AML in older patients is reflected by a higher proportion of patients with an unfavorable karyotype, a higher rate of primary drug resistance associated with overexpression of P-glycoprotein (P-gp), and an increased frequency of disease evolution from a preexisting and at time probably unrecognized myelodysplasia. Poorer tolerance of combination chemotherapy regimens leads to the use of less intensive treatment protocols (5). It is clear that several aspects of therapy in this group of patients require improvement. The development of new and effective anti-AML agents, however, remains a cornerstone of the continued efforts to improve the outcome of poor-prognosis patients. As the principal cause of treatment failure in older patients is resistant AML (manifested by short CR durations or failure to enter CR), investigational strategies should focus primarily on this problem and the introduction of new agents is warranted.

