2.3 Rationale for the Proposed Regimen in Elderly AML

Up to 50 patients older than age 65 with newly diagnosed AML were treated in the previously described Phase II studies under 2.2. The early results are impressive in terms of CR and marrow CR rates. In our institutional experience, 9 of the first 12 patients treated achieved remissions. This is significant in this elderly AML population. We are therefore proposing an investigator initiated IND study to gain further experience with different SGI-110 regimens. This will help in the Phase III design of the potential FDA pivotal trial which will evaluate SGI-110 based therapy versus best standard of care in patients who cannot tolerate intensive chemotherapy. We will restrict the evaluation in the study to patients 70 years or older, since there is little argument that such patients do not benefit from intensive anti-AML therapy. Since we do not know whether 5 or 10 days of hypomethylator therapy is better, we propose to include 2 arms, one using single-agent SGI-110 60mg/m² SQ daily x 5, and the second using SGI-110 60mg/m² SQ daily x 10. We wish also to explore, in this pilot experience SGI combinations. Anthracyclines are historically effective in AML; therefore a third arm will evaluate SGI-110 60mg/m² SQ daily x 5 with idarubicin at the low-dose 6mg/m² daily x 2. Finally, cladribine, an old drug with single-agent efficacy in AML, was found to be an effective hypomethylating agent. Therefore combining SGI-110 with cladribine at low-doses may improve the anti-AML and hypomethylation efficacy. The fourth arm will combine SGI-110 60mg/m² SQ daily x 5 with cladribine 3mg/m² daily x 5.

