6.0 Pretreatment evaluation

History and physical, CBC with differential and platelets, Chemistry profile (at least creatinine, SGOT or SGPT, total bilirubin) within 14 days of therapy start.

Bone marrow aspirate and/or biopsy within 30 days of therapy start. The bone marrow evaluation will include cytogenetic studies, if not done in previous 3 months.

Pregnancy (urine or blood) test for women of childbearing potential within two weeks of start of therapy. Child bearing potential is defined as not post-menopausal for 12 months or no previous surgical sterilization.

Baseline LVEF.

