10.0 Statistical Considerations

10.1.1 Update of the General Description/Sample Size February 01, 2017

This is a Phase II with 2 parallel arms study of SGI-110 in patients with newly diagnosed AML ≥ 70 years of age. The primary objective is to obtain an initial assessment of efficacy for the two SGI-110 regimens in this patient group:

- 1) SGI-110 single-agent for 5 days.
- 2) SGI-110 for 5 days combination with idarubicin for 2 days.

For each arm, we will enroll 20 patients. When all the arms have 20 patients then to be able to enroll more patients after the first 20 patients they have to satisfy the following rules: 1) there is more than 95% chance that the grade 3-4 non-hematological toxicity rate doesn't exceed 30%. 2) there is less than 10% chance that the 8-week mortality exceeds 15% and 3) there is more than 2.5% chance that the CR rate (CR+CRi) is more than 30%.

The arm or arms with the satisfying monitor rules above will continue to enroll an additional 20 patients. This will be decided through an interim analysis discussion with the Leukemia experts and the modality experts coordinating the study.

Complete Remission monitoring

The primary endpoint is the complete remission rate (CRR) evaluated after at least 2 cycles but would also be evaluated after 4 and 6 cycles if the patient is stable or improving. We have a target CRR of 30%, while a CRR of 15% is considered unacceptable. We will monitor complete remission using the Bayesian approach of Thall et al. [19]. The probability of complete remission

is denoted by P_{CR} . We assume $P_{CR} \sim \text{beta}(0.6, 1.4)$. Our stopping rule is given by the following probability statement: $\Pr(P_{CR} > 0.30 | \text{data}) < 0.025$. That is, we will stop the study if, at any time during the study, we determine that there is less than 2.5% chance that the CRR is more than 30%. This stopping rule will be applied in each arm. The stopping boundaries for complete remission, based on these assumptions and monitoring conditions are found in **Table 1**. We will apply these stopping boundaries starting from the first patient and in cohorts of 10. For example, accrual will cease if only 2 patients experiences complete remission among in the first 20 patients treated. The operating characteristics are summarized in **Table 2**. Both the decision rule and operating characteristics were calculated using the stopbound procedure in Stata version12.1.

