We will monitor 8-week mortality using the Bayesian approach of Thall et al. [19]. Following are the rules for the monitoring of 8-week mortality. The probability of 8-week mortality is denoted by P_M . We assume $P_M \sim \text{beta}(0.3, 1.7)$. Our stopping rule is given by the following probability statement: $\Pr(P_M > 0.15 | \text{data}) > 0.90$. That is, we will stop the study if, at any time during the study, we determine that there is more than 90% chance that the 8-week mortality is more than 15%. This stopping rule will be applied in each arm. The stopping boundaries for 8-week mortality, based on these assumptions and monitoring conditions is found in **Table 5**. We will apply these stopping boundaries starting from the first patient and in cohorts of 5. For example, accrual will cease if 3 patients died during the first 8 weeks among in the first 5 patients treated. The operating characteristics are summarized in **Table 6**. Both the decision rule and operating characteristics were calculated using the stopbound procedure in Stata version12.1.

Table 5. Stopping boundaries for Mortality (separately for each arm)

The number of patients evaluated for mortality	5	10	15	20	25	30	35	40
The number of patients died during the first 8 weeks	3	4	5	6	7	8	9	10

Table 6. Operating characteristics for Mortality Monitoring (separately for each arm)

True Mortality Rate	Early Stopping Probability	Sample Size		
		25 th percentile	Median	75 th percentile
0.05	0.0029	40	40	40
0.10	0.0298	40	40	40
0.15	0.1552	40	40	40
0.20	0.3790	20	40	40
0.25	0.6341	10	25	40

Statistical Analysis Plan

All patients who received at least 1 dose of the agent will be included in the intent-to-treat analysis for efficacy and safety. Demographic/clinical characteristics and safety data of the patients will be summarized using descriptive statistics such as mean, standard deviation, median and range (i.e. remission duration). Complete remission rates (CRR) will be presented with 95% confidence intervals. The association between CRR and patient and clinical characteristics will be

examined by Wilcoxon's rank sum test or Fisher's exact test. Survival time will be estimated using the Kaplan-Meier method. Patients who drop out of the study will be included in the time to event data as "censored data". The two-sided log-rank test will be used to assess the differences of time to events between groups.

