10.2 Treatment Assignment and Stopping Rules

Patients will be assigned to receive either of the 2 regimens. The randomization will be balanced 1:1 to each of the treatment arms.

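### Patients are randomised 1:1, but the plan specifies no between-arm estimate of complete remission and leaves karyotype out of the survival comparison; the cost is efficiency and interpretability, not bias

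*Combined protocol and SAP*

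**What the plan says.** Section 5.1 randomises patients between SGI-110 for 5 days (arm A) and the same SGI-110 schedule plus idarubicin (arm B). Section 10.2 adds: "The randomization will be balanced 1:1 to each of the treatment arms". No stratification factor is named.

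Section 10.1.1 sets a per-arm aim: "The primary objective is to obtain an initial assessment of efficacy for the two SGI-110 regimens in this patient group". On size it says "For each arm, we will enroll 20 patients", and then "The arm or arms with the satisfying monitor rules above will continue to enroll an additional 20 patients". The maximum is therefore 40 per arm, and expansion is decided separately for each arm. Tables 1 to 6 are all labelled as applying separately to each arm.

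The Statistical Analysis Plan in Section 10.1.1 says of the primary endpoint: "Complete remission rates (CRR) will be presented with 95% confidence intervals". It then relates remission to patient and clinical characteristics by Wilcoxon or Fisher tests. Treatment arm is not named there. Time-to-event endpoints get Kaplan-Meier estimates and a two-sided log-rank test between groups. The groups are not defined, and no hazard ratio, stratification or covariate is mentioned.

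On karyotype, Section 2.1 says that the different biology of AML in older patients is "reflected by a higher proportion of patients with an unfavorable karyotype", and gives this among the reasons for their worse outcome. Section 6.0 requires it at baseline: "The bone marrow evaluation will include cytogenetic studies, if not done in previous 3 months". No analysis uses it.

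**The concern.** Randomisation is what makes a comparison of the two arms trustworthy, and the arms differ in one component only. A reader will want to know what idarubicin adds to remission, and the plan gives no estimate of that. The likely substitute is to look at whether two separate intervals overlap, which is not a valid test of a difference and can point the wrong way.

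The survival comparison is planned, but loosely. With undefined groups and no hazard ratio, the method could be settled after the data are seen. Leaving out a baseline factor that the protocol itself links to outcome gives up some power and leaves a chance imbalance uncorrected, in a trial of at most 80 patients.

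**Working it through.** **1. The plan's own figures reproduce.** Inputs from Section 10.1.1: prior beta(0.6, 1.4); stop if Pr(P > 0.30 | data) < 0.025; looks in cohorts of 10. With x remissions in n patients the posterior is beta(0.6 + x, 1.4 + n − x). Pr(P > 0.30) is:

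| n | at the Table 1 boundary | one more remission |
|---|---|---|
| 10 | x = 0: 0.0065 | 0.0633 |
| 20 | x = 2: 0.0153 | 0.0564 |
| 30 | x = 4: 0.0152 | 0.0437 |
| 40 | x = 6: 0.0130 | 0.0330 |

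All four boundaries match Table 1. Exact binomial recursion over the looks at 10, 20 and 30 gives early-stopping probabilities of 0.5929, 0.3321, 0.1574, 0.0660, 0.0255 and 0.0094 at true rates of 0.15 to 0.40. Table 2 has 0.5994, 0.3303, 0.1528, 0.0670, 0.0255 and 0.0087, all within 1 point. The design is a sound pair of single-arm monitoring schemes. It states no between-arm effect, power or event count.

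**2. Precision of a difference in remission rate.** Half-width = 1.96 × √(2p(1 − p)/n), with the same rate p in both arms:

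| n per arm | p = 0.30 | p = 0.50 |
|---|---|---|
| 20 | 1.96 × √(0.42/20) = 0.284 | 1.96 × √(0.50/20) = 0.310 |
| 40 | 1.96 × √(0.42/40) = 0.201 | 1.96 × √(0.50/40) = 0.219 |

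**3. Power of such a comparison** (two-sided 5%, two-proportion normal approximation):

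| True rates | 20 per arm | 40 per arm |
|---|---|---|
| 15% vs 30% | 20% | 36% |
| 30% vs 50% | 25% | 44% |
| 30% vs 60% | 48% | 78% |

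For 80% power, 121 per arm would be needed for 15% vs 30%, and 93 per arm for 30% vs 50%.

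**4. Why two intervals are not enough.** Section 2.4 gives 7/8 (arm B) and 4/8 (arm A) at the 2017 update. The difference is 0.875 − 0.500 = 37.5 points, Newcombe 95% CI −7 to +68, Fisher p = 0.28: striking rates, but a difference compatible with none. The reverse can also happen. As an illustration, 23/40 vs 12/40 gives exact intervals of 41% to 73% and 17% to 47%, which overlap. The difference is 27.5 points, 95% CI +6 to +46, Fisher p = 0.024.

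**5. Chance of karyotype imbalance.** The documents give no prevalence. If 40% of patients are unfavourable (assumed), the exact binomial probability that the arms differ by 20 points or more is 26% at 20 per arm and 9% at 40. Over 20% to 50% prevalence it is 16% to 27% and 4% to 9%.

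**6. Cost to the log-rank test.** Simulation, 4,000 runs per setting, exponential survival, all events observed. Assumed inputs: treatment HR 0.5, karyotype HR 1.5 to 3, prevalence 20% to 50%. Power at 40 per arm, unstratified → stratified:

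| Karyotype HR | prevalence 20% | 35% | 50% |
|---|---|---|---|
| 1.5 | 0.844 → 0.841 | 0.824 → 0.828 | 0.825 → 0.831 |
| 2 | 0.824 → 0.837 | 0.792 → 0.830 | 0.785 → 0.829 |
| 3 | 0.782 → 0.838 | 0.739 → 0.832 | 0.709 → 0.836 |

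The gain runs from about 0 (0.841 − 0.844) to 13 points (0.836 − 0.709 = 0.127). At 20 per arm it runs from a loss of about 2 points (0.551 → 0.534) to a gain of 9 (0.433 → 0.525). With no treatment effect, both tests reject in about 5% to 6% of runs at either size.

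**The case against.** The strongest reply is that the trial never set out to compare the arms. The objective concerns each regimen, the benchmarks are fixed rates (30% wanted, 15% unacceptable), and every boundary is per arm. Per-arm rates with intervals answer that objective, and randomisation in such a phase II can serve simply to give similar patient groups. This stands, and it rules out two stronger readings.

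- A reader might infer that the trial wastes a comparison it was built to make, or that it exists to choose the phase III regimen. The documents do not support this. Section 2.3 says "This will help in the Phase III design of the potential FDA pivotal trial", but describes that trial as SGI-110 based therapy against best standard of care, and calls the present study a pilot. No comparative power is claimed, and a between-group log-rank test is planned.
- A reader might infer that an unadjusted log-rank test is biased. It is not: under randomisation it is valid, as the error rates of about 5% to 6% show.

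Other points also carry weight. Any reader can compute a crude difference from two reported proportions, and the interval will be wide. Section 2.1 offers karyotype as one of several reasons why older patients fare worse than younger ones, with no effect size at 70 and over; if its hazard ratio is 1.5, stratifying gains nothing. The protocol does not define an unfavourable karyotype, and at 20 per arm with 40% prevalence that stratum would hold about 8 patients per arm.

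What remains is an omission. The association tests for remission might be stretched to include arm, but the text does not say so, and a p-value is not an estimate. Leaving readers to derive the contrast also leaves open which patients enter it, which matters when the arms can expand separately.

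**Conclusion.** The point holds as one of efficiency and interpretability. The plan specifies no between-arm estimate for its primary endpoint. Its survival test names neither the groups nor an effect measure, and ignores a baseline factor that the protocol links to outcome and already collects. The plan's validity and its per-arm operating characteristics are not in question.

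The size is modest: about 0 to 13 points of log-rank power at 40 per arm. That rests on assumed karyotype hazard ratios of 1.5 to 3, prevalences of 20% to 50%, a treatment hazard ratio of 0.5 and complete follow-up, none of which the documents supply. The difference in remission rate would carry a half-width of 20 to 22 points at 40 per arm and 28 to 31 at 20 per arm, for common rates of 30% to 50%. It can describe the contrast and show how uncertain it is, but cannot serve as a powered test.

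**What to change.** Amend the Statistical Analysis Plan in Section 10.1.1 as follows.

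1. Keep the per-arm remission rates with their 95% CIs. Add the difference, arm B minus arm A, with a 95% CI, labelled exploratory, and state the expected half-widths (about 20 to 22 points at 40 per arm, 28 to 31 at 20).
2. Define the groups in the log-rank test as the randomised arms. Report a hazard ratio with 95% CI from a Cox model adjusted for karyotype, age and ECOG status, and give a karyotype-stratified log-rank test alongside the unstratified one.
3. Limit between-arm comparisons to patients randomised while both arms were open. If only one arm goes on from 20 to 40, its later patients have no concurrent randomised comparator; they still count in that arm's own rate.
4. Fix the karyotype grouping before analysis, with a category for missing or failed cytogenetics.

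This needs no extra patients, visits or tests: cytogenetics are required by Section 6.0, and age and ECOG status by Section 4.0. The cost is a little more analysis work, agreement on the karyotype categories, and a wide interval that must not be read as a powered comparison.

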2.4 Update of January 27, 2017

As of February 2017, 34 patients have been treated on study. The complete response in the 4 treatment arms are as follows: 4 out of 8 patients responded in the SGI-110 for 5 days arm; 5 out of 9 patients responded in the SGI-110 for 10 days arm; 7 out of 8 patients responded in the SGI+idarubicin arm and 3 out of 9 patients responded in the SGI+cladribine.

In addition, Astex, the sponsoring company, conducted a separate multi-institutional study of SGI-110 60mg/m² for 5 and 10 days in older patients with newly diagnosed AML who were not candidates for intensive chemotherapy (8). A total of 103 patients were treated, 51 patients were treated on the 5-day and 52 patients were treated on the 10-day regimens. The characteristics of the 2 study groups were well-balanced. Overall the CR rates were 19/51 = 37% on the 5-day regimen and 16/52 = 31% on the 10-day regimen. The overall response rates were 57% and 48%, respectively. The median survival were 10.5 months on the 5-day regimen and 9.5 months on the 10-day regimen ($p=0.70$). Side-effects, including myelosuppression, were similar in the 2 study groups. The 60-days all-cause mortality was also similar between the two study groups.

The study concludes that both schedules (SGI-110 given in 5-day and SGI-110 given in 10-day) were similar (8).

Based on the above findings, and after discussion with the Biostatistical collaborators, [name] and [name], it was decided to close the 2 arms of SGI-110 for 10 days (based on the Astex study) and SGI-110 + cladribine (low CR rate), and continue the study, with the same Bayesian statistical design, only in the 2 arms of SGI-110 for 5 days and SGI-110 + idarubicin.

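### Tests of which characteristics predict remission name no arm stratification and do not say whether arms are pooled; stratifying by arm would be a free, modest improvement to an exploratory analysis

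*Combined protocol and SAP*

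**What the plan says.** The statistical analysis plan at the end of Section 10.1.1 describes the analysis in a sentence that opens "The association between CRR and patient and clinical characteristics will be" and then gives the methods as "examined by Wilcoxon's rank sum test or Fisher's exact test". The analysis set is given just before: "All patients who received at least 1 dose of the agent will be included in the intent-to-treat analysis for efficacy and safety". No stratified test, regression model or arm term appears for this analysis. No significance level, hypothesis or sample size is attached to it. The text does not say whether the tests combine the arms or are run within each one. The monitoring rules for remission, toxicity and 8-week mortality, by contrast, are expressly applied arm by arm.

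Section 2.4 reports remission by regimen among the first 34 patients. For the shorter single-agent schedule it gives "4 out of 8 patients responded in the SGI-110 for 5 days arm"; for the longer one, "5 out of 9 patients responded in the SGI-110 for 10 days arm"; and for the two combinations, "7 out of 8 patients responded in the SGI+idarubicin arm and 3 out of 9 patients responded in the SGI+cladribine". The 10-day arm was then closed on the results of a separate study, and the cladribine arm because of its low remission rate. For the two continuing arms Section 10.2 says: "The randomization will be balanced 1:1 to each of the treatment arms". It lists no stratification factors. Each continuing arm enrols 20 patients, and 20 more if it meets the monitoring rules.

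**The concern.** If remission depends on regimen and the arms are pooled, leaving arm out of the test has two effects. First, the between-arm difference stays in the comparison and masks real predictors, so power falls. Second, a characteristic that happens to be commoner in the arm with more remissions picks up part of that arm's advantage and can look like a predictor.

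Patients from the closed arms, if included, add a further route. They all enrolled early, and 1:1 randomisation between the two remaining arms does not balance them against later patients. If the tests are instead run within each arm, confounding by arm disappears, but each test has at most 40 patients. An arm-stratified test uses all the patients without either weakness.

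What is at stake is a descriptive statement about which patients remit, and nothing that decides the trial.

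**Working it through.** **Figures to reproduce.** The plan gives no level, power or sample size for these tests. As a check on the surrounding remission design, Pr(P > 0.30 | x of n) under a Beta(0.6 + x, 1.4 + n − x) posterior, with cut-off 0.025, returns the Table 1 boundaries 0, 2, 4 and 6. An exact recursion with looks at 10, 20 and 30 gives early-stopping probabilities of 0.593 at a true rate of 15% (Table 2: 0.5994) and 0.066 at 30% (Table 2: 0.0670). The arm counts in Section 2.4 add up: 8 + 9 + 8 + 9 = 34.

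**How firm is the difference between regimens?** Exact 95% intervals:

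| Regimen | CR | Rate | 95% CI |
|---|---|---|---|
| SGI-110, 5 days | 4/8 | 50% | 16–84% |
| SGI-110, 10 days | 5/9 | 56% | 21–86% |
| SGI-110 + idarubicin | 7/8 | 88% | 47–100% |
| SGI-110 + cladribine | 3/9 | 33% | 7–70% |

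For the continuing arms (4/8 v 7/8), Fisher p = 0.28. For all four arms, the exact p = 0.18.

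**Tests compared.** The pooled Fisher test uses one hypergeometric distribution for the number of remissions among carriers of the characteristic. The stratified exact test uses the sum of the arm-specific hypergeometric counts, so both tests are exact. For a continuous characteristic, the pooled Wilcoxon test is compared with van Elteren: Σ(Wⱼ − Eⱼ)/(nⱼ + 1), with variance ΣVⱼ/(nⱼ + 1)², where Wⱼ is the rank sum of remitters in arm j.

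**Assumptions not in the documents.** A two-sided 5% level; a binary characteristic with 50% prevalence and within-arm odds ratio 3 to 5, or a normal characteristic with log-odds slope 0.6 to 1.0 per SD; 6,000 to 8,000 simulated trials per setting.

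**Power at 50% v 87.5%, 40 per arm.**

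| Effect | Pooled | Stratified |
|---|---|---|
| Odds ratio 3 (Fisher v exact) | 41% | 48% |
| Odds ratio 4 (Fisher v exact) | 59% | 66% |
| Odds ratio 5 (Fisher v exact) | 74% | 81% |
| Slope 0.6 (Wilcoxon v van Elteren) | 50% | 55% |
| Slope 0.8 (Wilcoxon v van Elteren) | 73% | 78% |
| Slope 1.0 (Wilcoxon v van Elteren) | 88% | 92% |

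A separate run at odds ratio 0.25 (the mirror image of 4) gave 56% v 64%. The exact-test gain is therefore 7 to 8 points. With only 20 per arm, odds ratio 4 gives 31% v 33%. At an assumed 37% v 60% with 40 per arm, the gain is about 0 to 2 points.

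**False positives, averaged over randomisation.** For a characteristic with no effect, at 50% v 87.5% and 40 per arm, pooled Fisher rejects 3.3% of the time and pooled Wilcoxon about 5%.

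**False positives given an imbalance.** The spurious difference in remission between carriers and non-carriers can be shown directly. With 26/40 carriers in the 87.5% arm and 14/40 in the 50% arm:

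- carriers: (26 × 0.875 + 14 × 0.50)/40 = 29.75/40 = 74.4%
- non-carriers: (14 × 0.875 + 26 × 0.50)/40 = 25.25/40 = 63.1%
- difference: 11.25 points, from arm alone

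At 24/40 v 16/40 it is 0.20 × 37.5 = 7.5 points. Rejection rates are:

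| Carriers by arm | Pooled Fisher | Stratified exact |
|---|---|---|
| 24/40 v 16/40 | 5.0% | 3.7% |
| 26/40 v 14/40 | 10.8% | 3.5% |
| 28/40 v 12/40 | 21.0% | 3.4% |

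At 37% v 60%, the 26/40 v 14/40 split gives pooled Fisher 6.2%. For a continuous characteristic whose arm means differ by 0.6 SD, at 50% v 87.5%, pooled Wilcoxon rejects 15.7% and van Elteren 4.8%.

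**How often do such imbalances arise?** With 50% prevalence, a gap of 20 points or more has a 9% chance with 40 per arm and 27% with 20 per arm. A gap of 30 points or more has a 1% and 8% chance respectively.

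**The case against.** The strongest reply is that pooling is inferred from silence. The sentence on dosed patients defines who is analysed, not that arms are combined, and the monitoring rules all work by arm. This stands: a reader might infer that the plan pools, but the text leaves it open. It does not remove the point, because tests within arm pay in sample size what pooled tests pay in confounding.

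Other stronger readings also fail:

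- **That remission is known to differ by regimen.** The counts are 8 or 9 per arm, with p = 0.28 and p = 0.18. Idarubicin v cladribine alone gives p = 0.0498, but that picks the best and worst of four arms after seeing the data.
- **That a 60% v 40% or 65% v 35% prevalence gap inflates error to about 9% or 15%.** Those figures arise when the arms are drawn from populations with different prevalences, which concurrent randomisation rules out. Fixed observed counts are the fair comparison, and 24/40 v 16/40 then gives about 5%.
- **That power falls by 12 to 15 points.** That sets an exact Fisher test against an asymptotic Cochran-Mantel-Haenszel (CMH) test. A substantial part of the gap is exact v asymptotic, not stratification.
- **That unequal arm sizes bias the test.** At 20 + 40 with common prevalence, pooled Fisher rejects 3.6%. Bias would need case mix to drift over time between patients who were not enrolled concurrently. The documents give no data to show or size this.
- **That Phase III planning rests on these tests.** Section 2.3 ties that planning to experience with the regimens, not to this analysis.

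That the analysis is exploratory also stands. It limits the weight of the point, but is no reason to ignore a recorded, randomised factor.

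**Conclusion.** The point holds as a minor one. The plan names tests without an arm term and leaves pooling unstated. A stratified test is at least as good in the settings examined and better in some. If arms are pooled and the continuing arms truly differ as 50% v 87.5% with 40 each, the power loss is about 7 to 8 points exact against exact, and 4 to 6 points for Wilcoxon. It is about 0 to 2 points if the arms are as close as 37% v 60%.

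The average false-positive rate is not inflated. It rises to about 11% only after an imbalance as large as 26/40 v 14/40 at the wider rate gap, or through calendar drift involving the closed arms. All of this rests on assumed effect sizes, 50% prevalence and a 5% level, none of which the plan states. The primary endpoint, its confidence intervals and the stopping rules are not touched.

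**What to change.** State in the analysis plan that each characteristic will be tested for association with CRR stratified by treatment arm:

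- **Categorical characteristics:** an exact stratified test, or CMH where counts allow.
- **Continuous characteristics:** the van Elteren test.
- **Alternative for either:** a logistic model for remission with arm as a term.

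Say whether patients from the two closed arms are included. If they are, give each closed arm its own stratum. Show the results by arm alongside the stratified result, labelled exploratory.

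The cost is a few lines of plan wording and a different test on the same data, with no extra patients, visits or data collection.
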